9.4.3 Sensitivity and Supplementary Analyses for Key Secondary Efficacy Endpoints

There are no additional supportive secondary efficacy analyses planned other than those described above.

9.5 Additional Efficacy Analyses

Additional efficacy endpoints will be compared between each risankizumab dose and placebo among the ITT Population at each visit in Period A.

Categorical endpoints will be analyzed, using the CMH test adjusting for the actual values of stratification factors. NRI-C will be the primary approach to handle missing data.

Continuous endpoints will be analyzed based on the fixed term of treatment from an MMRM model including the Baseline value and observed measurements at all post-baseline visits, adjusting for the fixed effects of treatment, actual values of stratification factors, visit and treatment-by-visit interaction as covariates.

Summary statistics will be provided for the additional efficacy endpoints at each visit in Period B by treatment groups. Categorical endpoints will be summarized by the number and proportion of subjects who achieved the endpoint, as well as the 95% confidence interval of that proportion. Continuous endpoints will be summarized by descriptive statistics including the mean, standard error, and the 95% confidence interval of the mean.

For efficacy endpoints of HS-related skin pain:

- Prohibited analgesic (including opioids): A subject will be counted as a non-responder from the day that the subject initiates prohibited analgesic to 5 days after the end of such analgesic use for categorical endpoints, and will have the last assessment prior to the initiation of analgesic carried forward until 5 days after the end of such analgesic use for continuous endpoints.
- Protocol-allowed analgesic use:
 - A subject who enter the study without concomitant analgesic will be counted as a non-responder from the day that the subject initiates a protocol-allowed analgesic to 2 days after the end of such analgesic use for categorical endpoints, and will have the last assessment prior to the initiation of analgesic carried forward until 2 days after the end of such analgesic use for continuous endpoints.

[figure not shown]
A subject who entered the study on a stable dose of a protocol-allowed concomitant analgesic will be counted as a non-responder from the first day of an analgesic dose increase to 2 days after the end of the dose increase for categorical endpoints, and will have the last assessment prior to the dose increase carried forward until 2 days after the end of such analgesic dose increase for continuous endpoints.

9.6 Efficacy Subgroup Analyses

To evaluate the consistency of the efficacy over demographic and other baseline characteristics, analyses will be performed for the following subgroups for the primary efficacy endpoint.

- Age group ($< 40 \text{ years}, \ge 40 < 65 \text{ years}, \ge 65 \text{ years}$)
- Sex (male, female)
- Race (white, non-white)
- Smoking (current, ex or never)
- BMI (normal: < 25, overweight: $\ge 25 < 30$, obese: ≥ 30)
- Duration of HS (by median)
- Baseline body weight (by median)
- Baseline CRP level (by median)
- Baseline AN count category (5-10, 11+)
- Prior exposure to TNF antagonists (yes, no)
- Prior exposure to biologic agents that block IL-12/23/17 (yes, no)
- Baseline Hurley stage (I, II, III)

In addition, the primary efficacy endpoint may also be summarized by anti-drug antibody (ADA) status and/or by neutralizing antibody (NAb) status, once the corresponding ADA and NAb data are completed.

10.0 Safety Analyses

10.1 General Considerations

Safety analyses will include adverse events, laboratory, and vital sign measurements.

Safety data will be summarized among the Safety_A and Safety_B populations by treatment groups. For the safety analysis, subjects are analyzed based on the actual treatment group, determined by the first dose of study drug that the subject received.

The overview of TEAEs, areas of safety interest (ASIs), and potentially clinically important (PCI) findings in laboratory variables and vital sign variables will be summarized among the ALL_RZB Population.

Missing safety data will not be imputed.

[figure not shown]
10.2 Adverse Events

Adverse events (AEs) will be summarized and presented using primary MedDRA System Organ Classes (SOCs) and preferred terms (PTs) according to the version of the MedDRA coding dictionary used for the study at the time of database lock. The actual version of the MedDRA coding dictionary used will be noted in the AE tables and in the clinical study report. When summarizing the number and percentages of subjects, subjects with multiple occurrences of the same adverse event will be counted once, and only the maximum severity level will be presented in the severity summaries, and the worst/highest relationship level in the relationship summaries.

10.2.1 Treatment-Emergent Adverse Events

Treatment-emergent adverse events (TEAEs) for each safety period are defined as follows:

Period A: A TEAE in Period A is defined as any event with an onset date on or after the first dose date of study drug in Period A and within 20 weeks (140 days) after the last

dose date of study drug in Period A, as long as it does not exceed the first dose date in Period B.

Period B: A TEAE in Period B is defined as any event with an onset date on or after the first dose date of study drug in Period B and within the minimum of (140 days after the last dose date of study drug in Period B, and the end of study date).

[figure not shown]
The All-Risankizumab Treated Period: TEAEs are defined in the following two groups:

- Any risankizumab: Any event with an onset date on or after the first dose date of risankizumab and within the minimum of (140 days after the last dose date of risankizumab, and the end of study date).
- **Risankizumab 360 mg:** Any event with an onset date on or after the first dose date of risankizumab 360 mg and the minimum of (140 days after the last dose date of risankizumab 360 mg, and the end of study date).

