## APPENDIX D. ACTIVITY SCHEDULE

The following table shows the required activities across the Screening, 6 Period A, 10 Period B, and Study Follow-up subject encounters. The individual activities and allowed modifications due to COVID-19 are described in detail in the **Operations Manual**.

Activity	Screening Day -35 to Day -1	Period A						Period B								Follow Up Call 20 Weeks after Last Dose
		Baseline/Week 0 Day 1	Week 1 Day 8	Week 2 Day 15	Week 4 Day 29	Week 8 Day 57	Week 12 Day 85	Week 16 Day 113	Week 17 & 18 Days 120 & 127	Week 20 Day 141	Week 28 Day 197	Week 36 Day 253	Week 44 Day 309	Week 52 Day 365	Week 60 Day 421	
Visit window		+/- 3 days						+/- 7 days								
INTERVIEWS & QUESTIONNAIRES																
Subject information and informed consent	✓															
Eligibility criteria	✓	✓														
Medical history	✓	✓														
HS history	✓	✓														
Demographics	✓															
Drug, tobacco (including e-cigarettes), and alcohol history	✓															
AE assessment	✓	✓	✓	✓	✓	✓	✓	✓	✓	✓	✓	✓	✓	✓	✓	✓
Prior/concomitant therapy (including prior use of biologics)	✓	✓	✓	✓	✓	✓	✓	✓	✓	✓	✓	✓	✓	✓	✓	✓
TB screening	✓												✓			
Patient Reported Outcomes (PGA Skin Pain and Analgesic Use)	✓	✓	✓	✓	✓	✓	✓	✓		✓	✓			✓		✓
Patient Reported Outcome (HSSA)	✓	✓		✓	✓	✓	✓	✓			✓			✓		✓
Patient Reported Outcome (HSIA)		✓				✓		✓			✓			✓		✓

Activity	Screening Day -35 to Day -1	Period A						Period B								Follow Up Call 20 Weeks after Last Dose	
		Baseline/Week 0 Day 1	Week 1 Day 8	Week 2 Day 15	Week 4 Day 29	Week 8 Day 57	Week 12 Day 85	Week 16 Day 113	Week 17 & 18 Days 120 & 127	Week 20 Day 141	Week 28 Day 197	Week 36 Day 253	Week 44 Day 309	Week 52 Day 365	Week 60 Day 421		Week 68/Premature Discontinuation Day 477
Visit window		+/- 3 days						+/- 7 days									
Patient Reported Outcomes (DLQI, EQ-5D-5L, WPAI, HADS)		✓						✓						✓		✓	
Patient Reported Outcome (PGIS)		✓				✓		✓		✓			✓				
Patient Reported Outcome (PGIC)			✓	✓	✓	✓	✓	✓		✓			✓				
Dispense handheld ePRO device	✓																
Collect handheld ePRO device																✓	
LOCAL LABS & EXAMS																	
Inflammatory lesion count (abscess, inflammatory nodule, and draining fistula count)	✓	✓	✓	✓	✓	✓	✓	✓		✓	✓	✓	✓	✓	✓	✓	
Hurley Stage	✓	✓						✓						✓		✓	
12-lead ECG	✓																
Height	✓																
Weight and waist circumference	✓																✓

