2.2 Study Design Overview

[figure not shown]
This is a Phase 2, multicenter, randomized, double-blind, parallel-group, placebocontrolled study to evaluate the safety and efficacy of 2 dose levels of risankizumab in adult subjects with moderate to severe HS diagnosed at least 1 year before the Baseline visit.

The duration of the study will be up to 85 weeks and will include an approximately 35-day screening period followed by 2 treatment periods.

- **Period A:** Subjects who meet the study's eligibility criteria (protocol Section 5.1) will be randomized at the Baseline visit, in a 1:1:1 ratio, to receive either risankizumab 180 mg or 360 mg via a subcutaneous (SC) injection, or matching placebo up to Week 16. Study drug administration for Period A will occur at Baseline, Weeks 1, 2, 4, and 12. The final efficacy evaluation of Period A will be at Week 16.
- **Period B:** Subjects who were initially randomized to placebo will then receive blinded risankizumab 360 mg at Weeks 16, 17, and 18, while subjects who were initially randomized to risankizumab will receive blinded matching placebo at the same time points to keep the treatment of Period A blinded. Starting at Week 20, all subjects will receive open-label risankizumab 360 mg every eight weeks (q8w), at Weeks 20, 28, 36, 44, 52, and 60. The final efficacy evaluation of Period B will take place at Week 68. A follow up call will be conducted approximately 20 weeks after last dose of study drug.

The schematic of the study is shown in Figure 1.

[figure not shown]
Figure 1. Study Schematic

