10.2.4 Treatment-Emergent Adverse Events per Patient-Years of Exposure

Exposure-adjusted TEAEs per 100 patient-years will be provided, where TEAEs per 100 patient-years of exposure are defined as the number of TEAEs divided by the total exposure in 100 patient-years.

Note that one event per preferred term per day per subject will be counted in the calculation of the number of TEAEs (i.e., a preferred term will not be counted twice on

the same day for the same subject). The exposure-adjusted TEAE rate per 100 patientyears is calculated as:

$$100 \times \frac{\text{Number of TEAEs}}{\text{Total Patient Years'}}$$

[figure not shown]
where total patient years in each period are defined below.

Total patient years in Period A: Sum of study drug exposure in Period A, defined as the minimum of (the last dose date in Period A + 140 days, the end of study date + 1 day, and the first dose date in Period B if not missing [and the cutoff date during the Primary Analysis + 1 day]) minus the first dose date in Period A, normalized by 365.25 and rounded to one decimal place.

Total patient years in Period B: Sum of study drug exposure in Period B, defined as the minimum of (the last dose date in Period B + 140 days, and the end of study date + 1 day [and cutoff date during the Primary Analysis + 1 day]) minus the first dose date in Period B, normalized by 365.25 and rounded to one decimal place.

Total patient years in the All-Risankizumab Treated Period:

- Any risankizumab: Sum of study drug of risankizumab exposure, defined as the minimum of (the last risankizumab dose date + 140 days, and the end of study date + 1 day [and cutoff date during the Primary Analysis + 1 day]) minus the first risankizumab dose date, normalized by 365.25 and rounded to one decimal place.
- **Risankizumab 360 mg:** Sum of study drug of risankizumab exposure, defined as the minimum of (the last risankizumab 360 mg dose date + 140 days, and the end of study date + 1 day [and cutoff date during the Primary Analysis + 1 day]) minus the first risankizumab 360 mg dose date, normalized by 365.25 and rounded to one decimal place.

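### The first Period B dose date falls in both the Period A and Period B TEAE windows, so same-day reactions to the Week 16 injection enter the placebo-controlled table under the wrong treatment

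*SAP*

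**What the plan says.** SAP 10.2.1 closes the Period A TEAE window at 140 days after the last Period A dose, "as long as it does not exceed the first dose date in Period B". It opens the Period B window with "any event with an onset date on or after the first dose date of study drug in Period B".

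For Period A person-time, SAP 10.2.4 takes the earliest of several dates, "and the first dose date in Period B if not missing", and subtracts the first Period A dose date. The end-of-study and cutoff dates in that formula each carry an extra day. The first Period B dose date does not. SAP 6.0 builds Period A treatment duration the same way, with 56 days in place of 140.

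On treatment, SAP 2.2 states: "Subjects who were initially randomized to placebo will then receive blinded risankizumab 360 mg at Weeks 16, 17, and 18". At those visits "subjects who were initially randomized to risankizumab will receive blinded matching placebo at the same time points". SAP 10.1 labels each subject in the safety tables by actual treatment, "determined by the first dose of study drug that the subject received". The placebo arm is therefore still labelled placebo on the day of its first active injection.

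**The concern.** A date equal to a limit does not exceed it, so the Period A rule would be programmed as onset on or before the first Period B dose date. The two windows then share one day. The SAP gives no tie-break by time of onset: it uses clock time only for baselines recorded on the ePRO device (SAP 9.1). The TEAE definition in protocol 7.4 covers the whole study and does not separate the periods.

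The shared day is an injection day on which the treatments cross over. The activity schedule (protocol Appendix D) lists adverse event assessment and in-clinic post-dose monitoring at Week 16, so same-day reactions are likely to be recorded. A reaction to risankizumab in the placebo arm enters the Period A placebo column. A reaction to the placebo injection in a risankizumab arm enters the Period A risankizumab column.

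Period A is the only placebo-controlled part of the safety data. The overview in SAP 10.2.2 tabulates adjudicated anaphylactic reactions and serious hypersensitivity by treatment group in each period. In a rare category of that kind, a single event can make the placebo column non-zero because of active drug.

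**Working it through.** The plan states no figure to reproduce. The check is on dates.

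**Inputs**
- Period A doses: "Study drug administration for Period A will occur at Baseline, Weeks 1, 2, 4, and 12" (SAP 2.2). The last falls on Day 12 × 7 + 1 = 85.
- First Period B dose: "Week 16 Day 113" (protocol Appendix D), which agrees with 16 × 7 + 1 = 113.
- Planned placebo arm: 74 (SAP 2.4, Table 1).
- Same-day reaction rate: not in the documents.

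**Which limit ends Period A**
- TEAE window: 85 + 140 = Day 225, later than Day 113.
- Treatment duration in SAP 6.0: 85 + 56 = Day 141, also later than Day 113.
- In each case the first Period B dose date sets the end.

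**Windows on schedule**

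| | Days covered | Length | Shared with Period B |
|---|---|---|---|
| Period A TEAEs as written | 1 to 113 | 113 | Day 113 |
| Period A exposure (SAP 6.0 and 10.2.4) | 113 − 1 | 112 | none |
| Period A TEAEs with a strict bound | 1 to 112 | 112 | none |

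The mismatch does not depend on visits being on schedule. If the first Period B dose falls on Day D, and that date sets the end of the period, the numerator covers D days and the denominator D − 1.

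**Size per misassigned case in the placebo arm**
- One subject: 1/74 = 1.35 percentage points. This is an upper limit, because SAP 10.2 counts a subject once per event. A subject with an earlier Period A event in the same category adds nothing.
- Person-time if all 74 reach Week 16: 74 × 112 / 365.25 = 22.7 patient-years.
- One event: 100 / 22.7 = 4.4 per 100 patient-years.

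**Range under an assumed same-day rate**

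| Assumed rate | Placebo subjects (74 × rate) | Added events per 100 PY |
|---|---|---|
| 1% | 0.7 | 3.3 |
| 3% | 2.2 | 9.8 |
| 5% | 3.7 | 16.3 |
| 10% | 7.4 | 32.6 |

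**Effect on the difference.** Let s(active) be the proportion of placebo-arm subjects newly counted because of the first active injection. Let s(placebo) be the proportion of a risankizumab arm newly counted because of the placebo injection. The risankizumab-minus-placebo difference changes by s(placebo) − s(active). It narrows only if s(active) is the larger, and only by the excess.

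**The case against.** The strongest case on the other side is that this is loose drafting with little consequence. Both exposure formulas stop at the first Period B dose date, which suggests that a strict cut-off was intended. The denominator mismatch is one day in 112 (0.9%), or 74/365.25 = 0.2 patient-years against 22.7, and it applies equally to all arms. The SAP never adds Period A and Period B counts. Injection site reactions are in neither the overview of SAP 10.2.2 nor the safety-interest list of Appendix B, and hypersensitivity enters the overview only when serious. Protocol 6.4 reports no identified concern with systemic hypersensitivity. All of this stands, and it keeps the point minor. It does not justify counting one day in both periods while excluding it from Period A exposure.

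A further objection concerns the remedy. Week 16 is also the final Period A evaluation, so an event that began that morning before the injection belongs to Period A. A strict date rule moves it to Period B. With dates alone, either convention misassigns some events. This also stands, and the fix allows for it.

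A reader might infer more than the documents support, in three ways:
- **That placebo incidence rises by a set amount, say 3 to 5 points, and that the contrast narrows by as much.** The documents give no same-day rate. Same-day events after the placebo injection are added to the risankizumab arms too, and repeat events in one subject do not count again.
- **That Period A is the only randomised safety comparison.** SAP 10.1 also summarises Period B by treatment group. What is unique to Period A is the placebo control.
- **That reactions to active drug disappear.** They are counted in Period B. For the placebo arm they are also in the all-risankizumab summary, whose window opens at the first risankizumab dose.

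**Conclusion.** SAP 10.2.1 is wrong as written. It assigns one day to two periods and contradicts the exposure formulas in SAP 6.0 and 10.2.4. On that day the placebo arm receives active drug and the risankizumab arms receive placebo, so the Period A columns can carry reactions to the other treatment.

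The size is at most 1.35 percentage points per misassigned placebo subject and about 4.4 per 100 patient-years per event, assuming that the planned 74 subjects all reach Week 16. The total depends on a same-day reaction rate that the documents do not give; the 1% to 10% range above is an assumption. The direction of the net effect also rests on an assumption, namely that same-day reactions to active drug outnumber those to the placebo injection.

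Severity is minor. The safety tables are descriptive, and no efficacy endpoint, significance level or power figure is affected.

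**What to change.** In SAP 10.2.1, change the upper bound of the Period A window to onset before the first dose date in Period B. Events and exposure then both cover 112 days on schedule, and no day is shared. Where adverse event onset time is collected, add that events beginning before the Week 16 injection stay in Period A.

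The cost is one phrase in the SAP and one inequality in the program. Without onset times, a few events that began on that date before the injection would move to Period B; a footnote to the Period A tables can say so.

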10.2.2 Adverse Event Overview

An overview of TEAEs by treatment groups in each period will be presented consisting of the number and percentage of subjects experiencing at least one event for each of the following AE categories:

- Any treatment-emergent AE
- Any treatment-emergent AE related to study drug according to the investigator
- Any severe treatment-emergent AE
- Any serious treatment-emergent AE
- Any treatment-emergent AE leading to discontinuation of study drug
- Any adjudicated MACE
- Any adjudicated anaphylactic reaction
- Any serious infection
- Any tuberculosis

- Any malignant tumor
- Any malignant tumor excluding NMSC
- Any serious hypersensitivity
- Any treatment-emergent AE leading to death

All deaths will also be summarized:

- Deaths occurring ≤ 140 days after last dose of study drug
- Deaths occurring > 140 days after last dose of study drug.

10.2.3 Treatment-Emergent Adverse Events by SOC and/or PT

[figure not shown]
Treatment-emergent adverse events will be summarized by SOC and PT; by maximum relationship to study drug as assessed by the investigator (e.g., reasonable possibility or no reasonable possibility) and by SOC and PT; by maximum severity and by SOC and PT; and by SOC and PT listing associated subject number. When summarizing the number and percentages of subjects, subjects with multiple occurrences of the same adverse event will be counted once, and only the maximum severity level will be presented in the severity summaries, and the worst/highest relationship level in the relationship summaries.

In addition, treatment-emergent adverse events will be summarized by PT and sorted by decreasing frequency for the active group.

10.2.4 Treatment-Emergent Adverse Events per Patient-Years of Exposure

Exposure-adjusted TEAEs per 100 patient-years will be provided, where TEAEs per 100 patient-years of exposure are defined as the number of TEAEs divided by the total exposure in 100 patient-years.

Note that one event per preferred term per day per subject will be counted in the calculation of the number of TEAEs (i.e., a preferred term will not be counted twice on

the same day for the same subject). The exposure-adjusted TEAE rate per 100 patientyears is calculated as:

$$100 \times \frac{\text{Number of TEAEs}}{\text{Total Patient Years'}}$$

[figure not shown]
where total patient years in each period are defined below.

Total patient years in Period A: Sum of study drug exposure in Period A, defined as the minimum of (the last dose date in Period A + 140 days, the end of study date + 1 day, and the first dose date in Period B if not missing [and the cutoff date during the Primary Analysis + 1 day]) minus the first dose date in Period A, normalized by 365.25 and rounded to one decimal place.

Total patient years in Period B: Sum of study drug exposure in Period B, defined as the minimum of (the last dose date in Period B + 140 days, and the end of study date + 1 day [and cutoff date during the Primary Analysis + 1 day]) minus the first dose date in Period B, normalized by 365.25 and rounded to one decimal place.

Total patient years in the All-Risankizumab Treated Period:

- Any risankizumab: Sum of study drug of risankizumab exposure, defined as the minimum of (the last risankizumab dose date + 140 days, and the end of study date + 1 day [and cutoff date during the Primary Analysis + 1 day]) minus the first risankizumab dose date, normalized by 365.25 and rounded to one decimal place.
- **Risankizumab 360 mg:** Sum of study drug of risankizumab exposure, defined as the minimum of (the last risankizumab 360 mg dose date + 140 days, and the end of study date + 1 day [and cutoff date during the Primary Analysis + 1 day]) minus the first risankizumab 360 mg dose date, normalized by 365.25 and rounded to one decimal place.

